**Fitbit-Only Control Group:**

Participants assigned to the Fitbit-only control study group you will not be receiving therapy. However, they will receive a Fitbit, which they will be asked to wear over the course of 16 weeks as well as to complete the same schedule of assessments as the therapy arms. One hundred participants will be randomized into this group.

Participation in this study can be added to an individual's regular course of treatment (such as medications) but should not replace ongoing treatment with his/her own doctor. Throughout participation in this study, the participant should continue any medications or treatments that his/her own doctor feels will best treat the symptoms of depression and/or cardiovascular disease.

#### **IV. RESEARCH DESIGN AND METHODS**

##### **Overview**

Given that majority of participants screened will not be eligible, we plan to screen 5000 individuals with the expectation that 10% will be eligible. We propose to recruit 500 eligible

patients from the ongoing MoodNetwork and the Health eHeart Alliance studies who self-report a history of depression and are at elevated risk for cardiovascular events. 40% of participants (2000) will be recruited from MoodNetwork, while 60% (3000) will be recruited from Health-eHeart. Participation will take a total of 16 weeks. During the first 8 weeks, participants will receive online CBT and a fitbit device to track activity, online MBCT and a fitbit device to track activity, or a fitbit device to track activity but no adjunctive therapy. The second 8 weeks are a follow-up period where participants will be asked to continue wearing their fitbit device, but receive no other form of treatment, regardless of which group they were initially randomized to. Participants will use desktop computers, laptops, tablet devices, or phones to participate in this study. These procedures are described in detail below.

Accessed through a links managed by MoodNetwork.org and Health-eHeart.org, interested participants will sign an online consent form waiver, found in a web portal hosted by the Eureka mHealth Research Platform. Eureka is a multi-tenant system (architecture in which a single instance of a software application serves multiple customers), which is housed on a HIPAA compliant Amazon cloud database. Once the participant has read and electronically signed the waiver of consent form, participants will register for Eureka and then complete a short battery of assessments to determine eligibility. The assessments will consist of 3 standard psychological assessments (The Patient Health Questionnaire [PHQ-9], the Altman Self-Rating Mania Scale [ASRM], and the Mini International Neuropsychiatric Interview [MINI], and 2 cardiac health assessments (The Duke Activity Status Index [DASI], and the International Physical Activity Questionnaire [IPAQ]). They will also be asked to complete a standard demographic form, and their medical and psychiatric histories. If they are not eligible, they will be thanked for their interest and informed that unfortunately, they are not eligible. If found eligible, they will provide their mailing address information so that we can ship them a Fitbit device. Once they receive their Fitbit device, they will return to the study portal to sync their fitbit with our system so that we can collect their step data complete a series of questionnaires, including the World Health Organization Composite International Diagnostic Interview for Bipolar Spectrum Disorders (CIDI), The Patient Health Questionnaire (PHQ-9), The Altman Self-Rating Mania Scale (ASRM), The Sheehan Disability Scale (SDS), The World Health Organization-5 Well-Being Index (WHO-5), the Self Efficacy for Exercise (SEE), the International Physical Activity Questionnaire (IPAQ), the Seattle Angina Questionnaire-7 (SAQ-7) and the Perceived Stress Scale (PSS). Once completed, participants will be randomized to CBT + Fitbit, MBCT + Fitbit, or the Fitbit-only control group. Those who are randomized to one of the two therapy-based treatment groups will be sent to a portal on MoodNetwork.org to access the interventions. Those randomized to the Fitbit-only treatment group will be brought to a page thanking them for their participation, reminding them to wear their fitbit for the next 16 weeks, and informing them that they will be emailed reminders when they need to return to the portal to complete surveys. All participants, regardless of study group, will be asked to return to Eureka in weeks 2, 4, 6, 8, and 16 to complete a battery of assessments and asked questions about adverse events that may have occurred since beginning the study (detailed in Table 1 below).

Participants in the two therapy-based intervention groups will receive either online CBT or online MBCT through a portal in MoodNetwork for 8 weeks. The therapy will consist of 25-40 minutes of weekly material. After this 8-week period, they will enter an 8-week follow-up phase during which no new treatment material will be administered, but they can access the material already presented during the treatment phase. If randomized to the control group, participants will wear the Fitbit device for an 8-week period and follow the same schedule of assessments as the treatment groups. Throughout the 16-week study, Fitbit data will be pulled into the Eureka mHealth Research Platform database, which is housed on a HIPAA compliant Amazon cloud database, using Fitbit's secure application programming interface (API). Coordinated and approved of by the Partner's Clinical Trial Office, Fitbit and MGH have agreed to a collaboration wherein Fitbit will share data (heart rate variability data and sleep data) with the study team that is collected with the devices, which is not available through their public API. Additionally, Fitbit will donate half of the devices needed for the study (275). In return, the study team will share de-identified assessment and summary data with Fitbit. Data will be transferred in a secure file sharing area (S3 Bucket) in Amazon cloud services. This has been documented in a donation agreement and a data use agreement.

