#### **b. Exclusion Criteria**

- Unwilling/unable to comply with study procedures
- Pregnant

- Responds to item 9 (Suicidal ideation) on the PHQ-9 with a 3 (i.e., “Thoughts that you would be better off dead or of hurting yourself in some way nearly every day”)
- Contraindications to exercise or diet interventions as assessed by the DASI
- Already uses a fitbit device or other activity monitor
- Suffers from repeated episodes of “blacking out” or “fainting”
- Survived a cardiac arrest
- Has recurrent chest discomfort with activity that goes away within 10 minutes of rest or with nitroglycerin
- Has heart failure
- Has been hospitalized recently (within past 6 weeks) for a cardiovascular problem

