**Table 1. Schedule of Assessments**

Weeks	0	1	2	4	6	8	16
	Pre				Mid	Post	Follow-Up
Demographics	X						
Medical/Psych Hx	X						
Mini International Neuropsychiatric Interview (MINI)	X						
World Health Organization Composite International Diagnostic Interview for Bipolar Spectrum Disorders (CIDI)		X					
Duke Activity Status Index (DASI)	X						
The Patient Health Questionnaire (PHQ-9)	X	X	X	X	X	X	X
Altman Self-Rating Mania Scale (ASRM)	X	X	X	X	X	X	X
Sheehan Disability Scale (SDS)		X		X		X	X
Well-Being Index (WHO-5)		X	X	X	X	X	X
Perceived Stress Scale (PSS)		X		X		X	X
Self Efficacy for Exercise (SEE)		X					

International Physical Activity Questionnaire (IPAQ) short form	X	X					
Cardiac Events	X	X	X	X	X	X	X
Seattle Angina Questionnaire – 7 (SAQ-7)*		X				X	X
Adverse Event Questions			X	X	X	X	X

\*The SAQ-7 will only be re-administered to those who respond affirmatively to having angina (coronary artery disease), heart attack, coronary bypass surgery coronary stent or angioplasty procedure or if participant has recurrent chest discomfort with activity that goes away within 10 minutes of rest or with nitroglycerin

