### **Protection Against Risks**

We will implement the following procedures to protect participants against risks:

1. Screening procedures will exclude any individuals who are not clinically suitable for the study protocol. For example, individuals will be excluded if they endorse a 3 on item 9 (Suicidal ideation) of the PHQ-9 (i.e., “Thoughts that you would be better off dead or of hurting yourself in some way p nearly every day”) during study intake. Lastly, to protect participants against risks, we will exclude individuals who have any contraindication to exercise or who are at elevated risk for a cardiac event as assessed by the DASI and Cardiac Events questionnaire.
2. Throughout the study, participants will be closely monitored for exacerbation of mental health conditions with the Patient Health Questionnaire (PHQ-9) and Altman Self-Rating Mania Scale (ASRM). Participants who score greater than a total score of a 20 on the PHQ-9 (indicative of “very severe” depression) and/or a total score of a 16 on the ASRM (or indicative of “very severe” mania) will be sent an automated message stating that their response on these assessments suggests that follow-up care with a local provider is warranted. If item 9 (Suicidal ideation) on the PHQ-9 is a 2 or higher (i.e., “Thoughts that you would be better off dead or of hurting yourself in some way on more than half the days”), then an automatic message will also be generated alerting the individual that their response warrants follow-up care with a local provider. Specifically, via embedded web links, we will refer participants to the MoodNetwork resource page and the DBSA “Find a Pro” link, and will encourage people to contact the National Suicide Prevention lifeline number ([name]) and/or online chat service if needed. When automated messages are sent, a flagged email will be sent to the PI, [name]. Based off the patient responses from the assessments, [name] and his fellow study clinicians will determine if it is safe for the participant to continue participating in the study.

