3. Patients will complete the brief, bi-weekly survey of potential cardiovascular symptoms (CE) to monitor participants throughout the study. The survey will ask patients whether they have been hospitalized for any of a variety of cardiac conditions. Patients who respond affirmatively to any of the components of the CE (specifically any of the choices 1-7 in question 1) will be automatically prompted to stop engaging in any excessive physical activity (including activity related to study) and to seek medical attention from their primary provider before proceeding. Study staff will be alerted in these situations and may follow-up directly with the participant.
4. Subjects may be withdrawn from the study for any of the following: 1; 1) Elevated risk for a cardiac event as confirmed by Cardiac Events assessment 2) Clinically significant or serious adverse event not consistent with continuation in study, as determined by subject or study clinicians; 3) Subject's decision to withdraw. Any subjects that are withdrawn from the study will be asked to contact their treating physician for any follow up care.

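### The suicidal-ideation message (PHQ-9 item 9 of 2 or higher) is not expressly applied to the screening PHQ-9, even for people excluded because they answered 3

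*Combined protocol and SAP*

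**What the plan says.** Section IV (Overview) places the PHQ-9 in the online battery that people complete after electronic consent and registration and before eligibility is decided. Table 1 lists it at week 0. The exclusion criteria include: "Responds to item 9 (Suicidal ideation) on the PHQ-9 with a 3". The Overview gives one outcome for everyone who fails screening: "If they are not eligible, they will be thanked for their interest and informed that unfortunately, they are not eligible".

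Section VI, Protection Against Risks, deals with intake and monitoring in separate items:

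- Item 1 concerns intake: "individuals will be excluded if they endorse a 3 on item 9 (Suicidal ideation) of the PHQ-9". No message or referral is attached.
- Item 2 opens "Throughout the study, participants will be closely monitored for exacerbation of mental health conditions". It sets the trigger at item 9 of 2 or higher, and "then an automatic message will also be generated alerting the individual that their response warrants follow-up care with a local provider". Provider and resource links, the suicide lifeline and a chat service go with that message. Each automated message also produces a flagged email to the principal investigator, after which the study clinicians "will determine if it is safe for the participant to continue participating in the study".
- Item 4 covers people who leave after enrolment: "Any subjects that are withdrawn from the study will be asked to contact their treating physician for any follow up care".

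**The concern.** The more severe answer may receive the lesser stated response. During the study, an item 9 answer of 2 brings up crisis links. At screening, an answer of 3 leads to exclusion, and the only stated communication is a notice of ineligibility. Withdrawn subjects are directed to their treating physician, but no matching sentence covers people turned away at intake.

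This is a patient-safety matter. Recruitment seeks people with a history of depression, so such answers are foreseeable. Screening is online, and the Overview describes no clinician contact. For an excluded person, week 0 is the only contact at which the message could be shown. Whether it appears should not depend on how a programmer reads the word *participants*.

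**Working it through.** No sample-size, power or error-rate figure bears on this point, so the check is mainly a comparison of text.

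**Which PHQ-9 triggers the message?**

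| Place | Situation | Stated response |
|---|---|---|
| IV, Overview | Ineligible for any reason | Thanks and notice of ineligibility |
| VI, Protection Against Risks, item 1 | Item 9 = 3 at intake | Exclusion |
| VI, Protection Against Risks, item 2 | Item 9 of 2 or higher, no visit named | Message, links, lifeline, chat, investigator email |
| VI, Protection Against Risks, item 4 | Withdrawn after enrolment | Asked to contact treating physician |
| VII.a, Safety and Monitoring | Participant safety discussions | Nothing stated for people screened out |

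Three features of item 2 point toward enrolled people. It speaks of monitoring over the course of the study for worsening, which presupposes a starting point. It ends in a decision about continuing, which does not exist for someone already excluded. Intake also has its own item. Against this, the trigger itself names no visit and no enrolment status. The text therefore supports two readings and does not choose between them.

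**A screenee who answers 2.** This answer does not exclude, because the threshold is 3. If the person is otherwise eligible, the next PHQ-9 comes only after the Fitbit has been shipped and received. If the message does not run at week 0, the first chance to show it is delayed until then.

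**Contacts available.** Table 1 lists the PHQ-9 at weeks 0, 1, 2, 4, 6, 8 and 16, which is 7 time points. A person excluded at screening completes 1 of the 7.

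**Scale.** The Overview plans to screen 5000 people and expects 10% to be eligible: 5000 × 0.10 = 500, leaving 5000 − 500 = 4500 expected screen failures. The 4500 is not the number at risk, because most will fail for other reasons or have low item 9 scores. The documents give no rate for item 9 = 3, so the rates below are assumptions:

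- 0.1%: 5000 × 0.001 = 5
- 1%: 5000 × 0.01 = 50
- 5%: 5000 × 0.05 = 250

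These are people excluded for that answer. How many of them would miss the message depends on which reading is implemented; under the broader reading it is none.

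**The case against.** The strongest reply is that item 2 already covers screening. Screenees consent and register before they complete the PHQ-9. The protocol calls them participants in the Overview and again under Participant Selection and Recruitment, where N is 5000. The list in Protection Against Risks is introduced as protecting participants, and its first item is screening. Week 0 is a scheduled assessment in Table 1. The item 9 trigger is unconditional, refers to the individual, and includes an answer of 3. The Overview is a workflow summary that mentions no automated safety message at any visit, so its silence about screening proves little. The screening screens and consent pages are not available, and crisis resources may appear there.

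Much of this stands. It rules out any claim that screenees are denied a referral, and it weakens the point about a screenee who answers 2, since that person has consented and may go on into the trial. The counts above are arithmetic on assumed rates and show no harm. But the reply establishes only that a second reading is available. It does not show that the protocol adopts it, and the references to worsening and to continuing in the study still lean the other way.

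**Conclusion.** The concern holds as stated: the plan does not expressly apply the item 9 message to the screening PHQ-9, including for people excluded because they answered 3. It should be fixed, because one of two plausible readings leaves a person who reports near-daily suicidal thoughts with only a notice of ineligibility.

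Confidence is medium, because the message may already run at week 0 in practice. The number affected cannot be estimated from the documents; the range of 5 to 250 rests entirely on assumed rates of 0.1% to 5%. The case does not depend on the number being large. Eligibility, endpoints, sample size and analysis are untouched.

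**What to change.** Add one sentence to the Overview in section IV and one to Protection Against Risks, item 2. Together they should say that the existing item 9 message and crisis links also run on the screening (week 0) PHQ-9, whether or not the person is eligible, and that they are shown together with the ineligibility notice when item 9 is 2 or higher. The threshold and message content stay as they are.

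Because item 2 ties the flagged investigator email to every automated message, the text should also state whether that email is sent for screenees. Sending it, and applying the PHQ-9 total-score or ASRM triggers at screening, can be left to the investigator.

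The cost is two sentences of protocol text and one display rule on the screening page; the message and links already exist. The one downside is that, if the email is kept for screenees, an action must be defined for people who are not enrolled. If the system already shows the message at week 0, the edit simply documents it.

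### Randomisation is triggered by completing the week 1 battery, and no stated step re-applies the safety exclusions to those answers, so a newly excluded person could be assigned

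*Combined protocol and SAP*

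**What the plan says.** The Overview in Section IV describes the entry sequence. After consent, people register and "complete a short battery of assessments to determine eligibility". The only eligibility decision follows: "If they are not eligible, they will be thanked for their interest and informed that unfortunately, they are not eligible". Eligible people give a mailing address, receive a Fitbit, return to the portal, sync the device and fill in a second set of questionnaires. Then: "Once completed, participants will be randomized to CBT + Fitbit, MBCT + Fitbit, or the Fitbit-only control group". The next step for the therapy arms is immediate: "Those who are randomized to one of the two therapy-based treatment groups will be sent to a portal on MoodNetwork.org to access the interventions".

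Two exclusions in subsection b of Section IV concern states that can change while a device is in the post: "Responds to item 9 (Suicidal ideation) on the PHQ-9 with a 3" and "Has been hospitalized recently (within past 6 weeks) for a cardiovascular problem". Neither carries a time point. Section VI, Protection Against Risks, item 1, ties the item 9 exclusion to study intake, a term the protocol does not define. The same item also excludes people who are "at elevated risk for a cardiac event as assessed by the DASI and Cardiac Events questionnaire".

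Items 2 to 4 of that section cover monitoring and withdrawal. An item 9 score of 2 or higher produces an automated referral message and a flagged email to the principal investigator, and study clinicians then judge whether continuing is safe. A positive Cardiac Events answer produces a prompt to stop excessive activity and see a provider, plus a staff alert; direct follow-up by staff is optional. Withdrawal is discretionary.

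**The concern.** The platform holds two sets of answers before assignment, but the stated flow uses only the first to decide who may enter. If the second set shows near-daily suicidal thoughts or a recent cardiovascular hospitalisation, the plan has disqualifying information in hand and no stated step that acts on it before allocation.

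The stake is mainly safety. In the therapy arms, such a person could be prompted to stop excessive activity and also be sent to a program intended to raise activity. There is a secondary cost in trial conduct: someone who should have been a screen failure may become a withdrawal after randomisation, and under intention to treat that person stays in the analysis population.

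**Working it through.** The claim concerns the order of procedures, so the check is a trace through the text. The plan gives no figure to reproduce.

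**Step 1: is the second battery the week 1 column of Table 1?** The Overview names nine instruments for the battery before randomisation: CIDI, PHQ-9, ASRM, SDS, WHO-5, SEE, IPAQ, SAQ-7 and PSS. All nine are marked at week 1, and CIDI and SEE are marked only there. The Overview lists the later returns as weeks 2, 4, 6, 8 and 16, without week 1, and the Adverse Event Questions begin at week 2. Week 1 therefore precedes assignment.

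**Step 2: is Cardiac Events collected then?** Table 1 has ten week 1 marks: the nine above plus Cardiac Events. The Overview does not name that survey, but its list is introduced as a partial one. The Cardiac Events row is marked in 7 of 7 columns, so a shifted table cell cannot explain the week 1 mark.

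**Step 3: which week 1 answers bear on an exclusion, and what does the plan do with them?**

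| Week 1 answer | Exclusion it can meet | Stated response | Holds assignment? |
|---|---|---|---|
| PHQ-9 item 9 = 3 | Exclusion Criteria; Protection Against Risks, item 1 | Message, flagged email, clinician review (item 2) | Not stated |
| Cardiac Events: hospitalisation | Exclusion Criteria (6-week rule); Protection Against Risks, item 1 | Stop prompt, staff alert, optional follow-up (item 3); possible withdrawal (item 4) | Not stated |

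**Step 4: is there a second eligibility branch?** None is stated. The Overview's single branch comes before shipping, and after the second battery the text goes straight to randomisation. The cardiac prompt tells the participant to seek care before going further; it does not instruct the platform to wait.

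**Step 5: scale.** The documents give neither the interval between the two batteries nor a rate of new positive answers, so no count can be derived. As a unit conversion only, each 1% of the planned 500 is 500 × 0.01 = 5 people, which under 200:200:100 allocation is 2 CBT, 2 MBCT and 1 control. This is not an estimate.

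**Step 6: effect on the comparison.** The answers precede assignment, so chance alone determines how these people fall across the arms. The trace gives no ground for bias between CBT and MBCT.

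**The case against.** The strongest reply is that week 1 is covered whichever way it is read. If it belongs to intake, the undated exclusions apply and an item 9 score of 3 already excludes. If it belongs to monitoring, Section VI prescribes a response, with an item 9 threshold of 2 that is stricter than the exclusion. The Overview is also a summary: it names Cardiac Events in neither battery, although Table 1 marks that survey at week 0 too, so its silence does not prove that no check is made.

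Much of this stands. A reader might infer that such a person would certainly be randomised. The documents do not support that, because the criteria are undated and study intake may extend to week 1. Nor may a reader infer that nothing protects the person. What remains is that, on either reading, no step applies the exclusion before allocation, clinician review has no stated deadline, and staff follow-up of a cardiac answer is optional.

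The Cardiac Events half is the weaker one. The form is not shown, so its look-back period and the content of its choices cannot be matched to the 6-week rule.

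A further objection is that an automatic block could displace clinician judgement for someone reporting near-daily suicidal thoughts. That is fair, and the change must keep the flagged email and the review.

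**Conclusion.** The concern holds as a possibility. Followed literally, the entry sequence could randomise a person whose answers already in hand meet one of the plan's own safety exclusions. This rests on reading the second battery as the week 1 column, which the instrument lists support well. For the cardiac part it also rests on the survey being able to reveal an exclusion, which Section VI implies but the unseen form cannot confirm.

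The number affected is unknown and probably small, and the existing alerts and review reduce the remaining harm. A reader might infer biased treatment effects or a meaningful loss of power. Neither follows: the answers precede assignment, and without a rate no loss of precision can be calculated. The gain is in safety, in agreement between the stated exclusions and the people assigned, and in fewer avoidable withdrawals. This is a cheap improvement, held with medium confidence.

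**What to change.** In the Section IV Overview, make assignment conditional on the week 1 answers:

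- Do not randomise if PHQ-9 item 9 is 3, or if a Cardiac Events choice shows one of the listed exclusions. The study clinicians should fix in advance which choices count.
- State that study intake runs up to randomisation, and name the Cardiac Events survey in the second battery.
- For anyone blocked, keep the automated referral message, the flagged email to the principal investigator and the clinician review. For a cardiac answer, also keep the stop prompt and the staff alert.
- Leave scores that are not exclusions (item 9 of 2, PHQ-9 total above 20, ASRM of 16) under the existing monitoring, without delaying assignment.

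The change needs a rule on answers already collected, a one-time list of Cardiac Events choices, and brief protocol wording. Each blocked person costs one mailed device and one replacement to reach 500. That person also leaves the study's repeated PHQ-9 monitoring, as any screen failure does, which is why the referral and review must remain.
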